### **Aim 2. Explore the relationships of how diverse groups differentially use VR technologies and how PROs correlate with quantized qualitative data.**

To achieve this aim, we will quantize the qualitative data derived from interview transcripts by calculating the frequency of qualitative code reoccurrences within each participants' interview transcripts. Then, we will correlate the entire sample's quantized count data with their corresponding PRO scores as recorded in the parent study. To account for the non-normal, discrete nature of the count data, we will calculate Spearman's rho to assess the strength and directionality of the relationship between the constructed codes and the PRO scores (see Figure 1 below for power justification). Codes that are found to have a significant correlation with the PRO scores will be compared between the demographic subgroups of interest. This shall be performed through a combination of visual analysis and Kruskal-Wallis tests (when sample size allows).

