These individuals will subsequently be randomized into two groups to participate in a one-on-one (1:1) semi-structured interview exploring their beliefs and experiences of the VR intervention during their time in the parent study. Considering the subject and focus of this interview, no PHI is intended to be asked of the participants nor recorded for the purposes of this study. The first group will have standard 1:1 semi-structured interviews led by a trained social scientist. Participants in the second group will also have 1:1 semi-structured interviews, but these interviews will be led by an artificial intelligence (AI)-powered virtual social scientist. This AI interviewer is a version of GPT4 that has been iteratively refined by the study team to follow best practices in conducting 1:1 semi-structured interviews through prompt parameters. The refined prompt parameters and set interview questions will be automatically given to GPT-4 upon each initialization of the GPT4-powered AI interviewer. These prompt parameters and interview guide are set or "locked", as it is not intended for the purposes of this investigation to implement revisions or improvements of the AI interviewer based on the data received during any of the interviews. Regarding collected data, all information collected during the interview (e.g., interview transcripts) and all data uploads/downloads between the interview software and GPT4 will be encrypted, transmitted, and stored in Microsoft Azure services with whom we have an executed business agreement that all data storage will meet or exceed HIPAA requirements.

Transcripts created by this process will be coded and analyzed independently by both AI and human social scientists. This analysis will follow a general, open-coding approach wherein first level codes will be created inductively from the data with refined second-level codes created from the first level. Results yielded from these analyses will be compared qualitatively to assess the thematic coverage, breadth and overlap between the results generated by the AI and human social scientists.

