A later analysis will use only the second-level codes generated by the human social scientists. The human-generated second-level codes will be quantized by calculating their frequencies of occurrence in each transcript. These code frequencies will be used to identify qualitative factors that may be correlated with the participants' PRO data from the parent study. Additionally, we will compare how these significant factors and the overarching qualitative themes differ across the demographic groups of interest. Successful completion of this supplemental study will guide future VR development and research to be more inclusive of and sensitive to diverse racial/ethnic, socioeconomic, geographic, gender, and age populations. Finally, we will evaluate the feasibility of using an AI-powered virtual social scientist to both collect and analyze qualitative data.

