### **Aim 3. Investigate the feasibility of AI to conduct 1:1 semi-structured interviews.**

To achieve this aim, participants will be randomly assigned to one of two groups that are differentiated by the type of interview they will receive. In one group, participants will have a 1:1 semi-structured interview via Zoom with a human social scientist that is trained in qualitative interview approaches ([name]). The other group shall undergo the same process but with a virtual AI-powered interviewer whose avatar and voice will come across through Zoom. Both groups will be interviewed using the same set of probe questions for a maximum time per interview of 60 minutes. Only the audio from the interviews will be recorded and subsequently transcribed. Upon completion of the interviews and subsequent transcription process, all the transcripts will undergo qualitative data analysis by both AI and trained human social scientists independently. As such, this qualitative data analysis is expected to yield two sets of results that are respective to the analyst type (AI and human). Following completion of the interview, participants will be asked to complete a 10-item "Interviewer Sentiment Scale" questionnaire, delivered through REDCap. These results will be compared qualitatively for differences in thematic breadth and depth as well as the comparison of inductively created codes between the two results sets.

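### Appendix C, Aim 2 selects codes by unadjusted tests on raw counts per transcript, with no allowance for transcript length or the number of codes tested

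*Protocol*

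**What the plan says.** Section 13.1 of the protocol says that second-level codes produced by the human analysts will be "quantized by calculating their frequencies of occurrence in each transcript". Section 13.2, Aim 2 repeats this ("calculating the frequency of qualitative code reoccurrences") and treats the result as a count: "To account for the non-normal, discrete nature of the count data, we will calculate Spearman's rho". Both interviewer groups are pooled: "we will correlate the entire sample's quantized count data with their corresponding PRO scores as recorded in the parent study".

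The selection rule follows: "Codes that are found to have a significant correlation with the PRO scores will be compared between the demographic subgroups of interest". Those comparisons use graphs and, where numbers permit, Kruskal-Wallis tests.

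The number of codes is open, because "first level codes will be created inductively from the data with refined second-level codes created from the first level". Interview length is open as well. Aim 1 makes the interviews semi-structured to allow open dialogue, and Aim 3 sets only a ceiling: "Both groups will be interviewed using the same set of probe questions for a maximum time per interview of 60 minutes". Participants are randomised to a human or an AI interviewer; no allocation ratio is given.

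The sample is at least 30 (section 13.2) and at most 35 (section 13.1). Appendix C states no significance level, so the default in section 9.4.1 (two-sided 0.05) is taken to apply. SAP version 3.0 is dated September 2021 and Appendix C was added in September 2023; the SAP does not mention it. SAP section 6.3 leaves exploratory tests outside gatekeeping.

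**The concern.** Two features of the filter can let through codes that have nothing to do with the PRO.

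The first is chance. Each code gets its own test, the number of tests is decided by the coding, and passing at the nominal level is enough to go forward. More than one PRO would add further tests.

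The second is exposure. A longer transcript gives any code more opportunities to appear. If participants with worse (or better) scores tend to talk for longer, counts of unrelated codes drift with the score in the same direction. Spearman's rho deals with the shape of the count distribution, which is the only reason the plan gives for choosing it. It does not deal with unequal transcript length.

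What is at stake is the content of Aim 2. The selected codes are meant to show which factors help or hinder the therapy in different demographic groups and to inform later VR development. Codes chosen by chance or by talkativeness would be interpreted as substantive.

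**Working it through.** **Plan's own figure.** The only quantitative support is a power curve for Spearman's rho at n=30, which is not shown in the available text. There is no stated error rate to reproduce.

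**Step 1: what counts as significant.** At n=30 and two-sided 0.05, t(28) = 2.048, so the critical value is |rho| = 2.048/√(28 + 2.048²) = 0.36.

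**Step 2: chance alone.** For K independent codes with no true association and one PRO, P(at least one false code) = 1 − 0.95^K, and the expected number of false codes is 0.05K. K is an assumption; the documents do not give it.

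| K | P(at least one) | Expected false codes |
|---|---|---|
| 5 | 1 − 0.95^5 = 23% | 0.25 |
| 10 | 1 − 0.95^10 = 40% | 0.5 |
| 20 | 1 − 0.95^20 = 64% | 1.0 |
| 30 | 1 − 0.95^30 = 79% | 1.5 |

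This step needs no assumption about transcript length. Positive dependence between codes would lower the middle column but not the last one.

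**Step 3: transcript length.** Simulation with n=30, lognormal transcript length with CV 40%, expected count proportional to length, and no link between code and PRO once length is given. All these settings are assumptions. In the Poisson case participants differ in code use only through length. In the overdispersed case they also differ in how often they raise a theme (negative binomial, shape 2 or 1). The entries are the percentage of null codes declared significant, over mean counts of 5 and 10.

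| Length–PRO correlation | Poisson | Overdispersed | After length adjustment |
|---|---|---|---|
| 0 | 5 | 5 | about 5 |
| 0.2 | 10–12 | 6–7 | about 5 |
| 0.4 | 25–35 | 9–13 | about 5 |

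Length adjustment means either a rate per unit length or a partial Spearman correlation given length; both behave the same way here.

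A second set of runs used 20 null codes, a mean count of 5, a different degree of overdispersion and length CV of 40% or 70%. It gave 9–13% per code at correlation 0.3 and 16–29% at 0.5.

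**Step 4: is either remedy enough alone?** No. In the second set of runs, length adjustment restored the per-code rate to 5–6%, but the chance of at least one false code among 20 stayed at 64–70%. A multiplicity rule alone would not help if the individual p-values were already distorted by length.

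**Step 5: interviewer type.** With AI-led transcripts half as long as human-led ones and length otherwise unrelated to the PRO, the per-code rate stayed at 5%.

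**The case against.** The best defence is that this is a small, qualitative-led, embedded design. Aim 2 is presented as exploration, selected codes are afterwards examined for context and content, and none of it enters the trial's efficacy inference. Strict error control with 30 to 35 participants is expensive, and many analysts would simply report rho with confidence intervals. That stands as an argument about severity. It does not rescue the stated rule, which uses significance as a gate and draws interpretive conclusions from whatever passes.

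It is also fair that inflation from length is conditional. If length and PRO are unrelated the per-code rate is 5%, and nothing in the documents says whether they are related. The common probe questions and the time limit should narrow the spread of lengths. Strict proportionality between second-level codes and length is an assumption.

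Three stronger readings are tempting and are not supported:

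- **A reader might infer that ignoring interviewer type creates false codes.** Assignment is randomised, and the qualifying Pain Interference survey (Day 60, or week 8 in the companion study) is completed before the interview. Omitting interviewer type adds noise and a possible chance imbalance, not systematic bias. Nor may one say that half the interviews are AI-led, because the ratio is not given.
- **A reader might take 35% or 79% as the expected error.** The first needs pure Poisson counts and a length–PRO correlation of 0.4; the second needs 30 independent codes. Each is the top of a range.
- **A reader might conclude that counts should simply be replaced by rates.** Someone who met more barriers may speak longer because of them. Dividing by length would then remove real signal, and the simulation, which assumes no such link, cannot show that loss.

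**Conclusion.** The concern holds as a modest point about an exploratory sub-study. The two omissions, of length and of multiplicity, are plain in the text, and the SAP does not fill them. The chance component depends only on the number of codes and their dependence: 23% to 79% for 5 to 30 independent codes. The length component depends on an unobserved relation: no inflation at zero correlation, about 6–12% per code at 0.2, and 9–35% at 0.4, given n=30, length CV 40% and the count models above. Interviewer type is not a further cause. The trial's efficacy results do not use this analysis.

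**What to change.** In section 13.2, Aim 2:

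- Report for each code the raw Spearman rho with a confidence interval and, beside it, a length-adjusted one: either the rate per 1,000 participant words or the partial Spearman correlation given word count. Stratification by interviewer type is an optional refinement to reduce noise.
- Name the PROs to be tested, and carry codes forward on a false-discovery-rate-adjusted p-value across all codes and PROs tested.
- Label any code taken forward without adjustment as hypothesis-generating.

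**Cost.** A few sentences and a little analysis; word counts come from transcripts already planned. Fewer codes will pass. As an upper guide to the loss, take Bonferroni for 20 codes (0.05/20 = 0.0025 per test) at n=30 and a true rho of 0.5. With the Fisher z approximation, power is Φ(atanh(0.5)/SE − z), where SE = √(1/27) or √(1.06/27). It falls from 79–81% for a single test to 40–43%. A false-discovery-rate limit is milder, which is why it is preferred here. Length adjustment may also remove some genuine signal, so both versions should be shown.

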#### Approach

An NIH commissioned report on a “best practices” approach of mixed methods research (MMR) described MMR as “focusing on research questions that call for real-life contextual understandings, multi-level perspectives, and cultural influences...It is a systematic and rigorous form of inquiry that uses

methods of data collection such as in-depth interviews, ethnographic observation, and review of documents."

In this supplemental study, we will conduct MMR employing NIH best practice methodology to better understand the barriers to VR implementation and the appropriateness of VR content across diverse cultures. This process will follow an embedded mixed methods design (QUAL(quan)) in which we will sample up to 35 individuals who have completed their participation in the skills-based VR therapy treatment arm of either the parent study (STUDY00000631) or another concurrently running study that employs the same intervention in its treatment arm (STUDY00001262). We plan to sample from this additional source (STUDY00001262) to ensure the maximal sampling of the targeted subgroups as identified by this supplement.

Potential subjects will be identified and considered eligible for participation in this study based on their current timepoint of participation within the respective study they are currently enrolled in (STUDY00001262 or STUDY00000631). For the parent study (STUDY00000631), this is defined as any participant in the active treatment arm that has completed their day 60 PROMIS Pain Interference survey. For the concurrently running study (STUDY00001262), this is defined as any participant in the active treatment arm that has completed their week 8 PROMIS Pain Interference survey. The rationale for these criteria is the time-equivalency of data points, as this measure shall be used in further analyses within this supplemental study. The other criterion for eligibility is that the individual is 18 years or older. All participants that meet these criteria will be considered for participation in this sub-study.

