## 13.2 AIMS AND METHODOLOGY

### **Aim 1: Understand any barriers to implementing therapeutic VR technologies across diverse populations and learn how cultural differences influence perception of the VR content.**

[figure not shown]
To achieve this aim, we will interview a subset of participants by employing purposive sampling; participants who were enrolled in the skills-based VR arm of the parent study will be chosen based on criteria to maximize diversity across race/ethnicity, socioeconomic brackets, geography (based on zip-code: rural and non-rural), gender, and age. Interviews will be performed via Zoom video conferencing platform, and only the audio (not video) of the interviews will be captured. Interviews will be semi-structured to accommodate open, constructive dialogue. Prior to the first interview, we will develop a guide for interviewers that includes participant instructions, open-ended questions, and scripted probes to expand on themes. Interview questions will be tailored to target what barriers interviewees experienced while using VR and how they perceived the VR content in terms of their own cultural framework. Each interview is expected to last no more than 60 minutes. The audio recordings will be transcribed for subsequent analyses. Each subgroup will attempt to include at least five participants; to accommodate this diversity, at least 30 subjects will be recruited. Recruitment will continue until 1) at least 30 subjects have been interviewed and 2) thematic saturation has been established as defined by 3 consecutive interviews with no new emergent themes.

Upon completion of the interviews, trained social scientists will perform a general qualitative analysis via the open coding of the transcripts using ATLAS.ti software, including coding of participant language and classification of vocabulary into major and minor concepts. The evaluation process will generate recurring key words, phrases, and quotes, which can further be divided and compared among the subgroups. All participants will be assigned to five subgroups: race/ethnicity, socioeconomic bracket, geography, gender, and age. For each of these subgroups, we will use ATLAS.ti to generate code count histograms within major and minor concepts and will develop a network to depict a framework describing the breadth and depth of concepts. The result will identify differences among the subgroups and provide feedback for developing future, more inclusive VR content.

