**Figure 1: Power Estimate for Spearman Correlation at n = 30**

Finally, we will complete the qualitative analysis process by constructing overarching cross-group themes that illustrate the views, opinions, and experiences of utilizing the skills-based VR intervention. This process will also include an exploration of how both the significantly correlated qualitative codes and the cross-group themes differ in context and content across the demographic subgroups of interest.

By following this process, we hope to identify demographic-specific factors that both promote and inhibit the therapeutic efficacy of skills-based VR pain management. Awareness of these relationships will be necessary for improving the equity and inclusiveness of future VR therapeutics.

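### Appendix C Aim 2 correlates interview codes with a follow-up pain score without a baseline term, so a code that only marks worse starting pain can be taken as one that inhibits benefit

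*Protocol*

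**What the plan says.** Appendix C is an interview sub-study of people given skills-based VR. Section 13.1 (Approach) sets the upper sample size: "we will sample up to 35 individuals who have completed their participation in the skills-based VR therapy treatment arm", from the parent study or a concurrent study of the same intervention. Section 13.2 Aim 1 sets the lower: "at least 30 subjects will be recruited".

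For parent-study participants, eligibility in section 13.1 depends on one survey: "this is defined as any participant in the active treatment arm that has completed their day 60 PROMIS Pain Interference survey". The concurrent study uses its week 8 survey. The reason given is "The rationale for these criteria is the time-equivalency of data points, as this measure shall be used in further analyses within this supplemental study".

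Section 13.2 Aim 2 contains the only quantitative step that links codes to outcome: "we will correlate the entire sample's quantized count data with their corresponding PRO scores as recorded in the parent study", and "we will calculate Spearman's rho to assess the strength and directionality of the relationship between the constructed codes and the PRO scores". Codes that reach significance are then compared between demographic subgroups, by eye and by Kruskal-Wallis tests. The closing paragraph of Aim 2 states the purpose: "we hope to identify demographic-specific factors that both promote and inhibit the therapeutic efficacy of skills-based VR pain management".

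Appendix C mentions no baseline score, change score, covariate or partial correlation. In the main trial, the Day 30 analysis (Protocol 9.4.2), the Day 60 and 90 analysis (9.4.3) and the refitted subgroup models (9.4.7) all use change from baseline with the baseline score as a covariate.

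**The concern.** Therapeutic efficacy concerns how much people improve. A follow-up score combines improvement with starting severity. The interviews ask about barriers met while using VR, and people who began with worse pain may speak more often of difficulty or discomfort. If so, such codes would correlate with a high Day 60 score through severity alone. Higher PROMIS Pain Interference means more interference, so the correlation would be positive, and given the stated aim it could be taken as a sign that the factor inhibits benefit.

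The intended interviewees come from one treatment arm, so no comparator separates severity from response. Flagged codes pass into the demographic comparisons, so a severity artefact could carry through to the sub-study's conclusions about which groups benefit and why.

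**Working it through.** **Plan's own figure.** The only figure attached to this analysis is the Figure 1 power curve for a Spearman correlation at n = 30. The image is not available and the text gives no value, so there is nothing to reproduce.

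**Inputs from the documents.**
- n = 30 (minimum) and 35 (maximum), sections 13.2 and 13.1.
- Two-sided 0.05, the general rule in Protocol 9.4.1. Appendix C states no level of its own.
- Baseline is the screening-week value (9.4.1), so it exists for parent-study participants.

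**Inputs assumed.**
- r, the correlation between a code's underlying score and baseline pain: 0 to 0.7.
- ρ, the correlation between baseline and Day 60 pain: 0 to 0.7. Protocol 9.2 uses a correlation of 0 between baseline and Day 30, but only as a conservative sizing value.

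**Null tested.** The code relates to baseline only and has no link to the Day 60 score once baseline is known.

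**Formulas.**
- Expected correlation of the code with the Day 60 score: r × ρ.
- Partial correlation on ranks, with K = code count, Y = Day 60 score, B = baseline: (r_KY − r_KB × r_YB) / √[(1 − r_KB²)(1 − r_YB²)], tested on n − 3 degrees of freedom.
- Smallest significant correlation at n = 30: t / √(n − 2 + t²) with t = 2.048, so 2.048 / √(28 + 4.19) = 0.36. For 80% power the true correlation must be about 0.49 to 0.50.

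**Simulation.** 10,000 samples per setting, code counts with mean 2. Results at n = 30:

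| r | ρ | r × ρ | Mean simulated Spearman, Day 60 score | Flagged, plain | Flagged, partial given baseline |
|---|---|---|---|---|---|
| 0.3 | 0.5 | 0.15 | 0.135 | 11.0% | 5.3% |
| 0.3 | 0.7 | 0.21 | 0.188 | 17.2% | 5.0% |
| 0.5 | 0.5 | 0.25 | 0.228 | 23.5% | 5.7% |
| 0.5 | 0.7 | 0.35 | 0.320 | 42.3% | 5.4% |
| 0.7 | 0.5 | 0.35 | 0.320 | 42.0% | 5.3% |
| 0.7 | 0.7 | 0.49 | 0.450 | 73.6% | 5.8% |

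At ρ = 0.3 the plain rates are 6.9%, 11.3% and 18.0% for r = 0.3, 0.5 and 0.7. If r or ρ is zero, the plain rate is 4.7% to 5.2%. At n = 35 the plain rates are slightly higher: 12.1% (r = 0.3, ρ = 0.5), 27.6% (0.5, 0.5), 48.8% (0.5, 0.7) and 80.6% (0.7, 0.7), against 5.0% to 6.1% with adjustment.

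**Sensitivity to the count model.** With noisier counts (Poisson around a latent score, latent link 0.5), the plain correlation flags 16%, 22% and 27% at ρ = 0.5, 0.6 and 0.7. Adjustment again gives 5% to 6%. In that model, power for a code truly linked to the baseline-adjusted outcome is 40%, 34% and 27% plain, and 48%, 47% and 45% adjusted. At ρ = 0 adjustment costs almost nothing (50% against 49%).

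**A simple change score does not solve it.** With equal SDs, the code's expected correlation with change is −r × √[(1 − ρ)/2]. At r = ρ = 0.5 this is −0.5 × √0.25 = −0.25. The simulation gives −0.227 and flags 22.9%, now in the opposite direction, through regression to the mean.

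**The case against.** The strongest reply is that this reads more into the text than it states. Aim 2 speaks only of PRO scores; Day 60 and the raw form come from reading it with the eligibility paragraph in 13.1, and a change score is not ruled out. This stands, and it is why the fix begins by naming the outcome. It does not remove the problem, because an unadjusted change score is biased the other way.

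Second, no rule in the plan labels a code as promoting or inhibiting. The aim is exploratory, a Spearman correlation does describe how PROs relate to codes, and the efficacy sentence is worded as a hope. A reader might infer that the plan will label severity markers as inhibitors. The documents support only that such a code can be taken that way.

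Third, a reader might infer that a Day 60 score mostly repeats baseline. The documents give no such correlation, and at ρ of 0.5 to 0.7 baseline explains 25% to 49% of the variance (0.5² and 0.7²). Nor do they show that codes about barriers and cultural perception track pain severity. The size is therefore unknown, and a range is all that can be given.

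Fourth, the null used here is no link to Day 60 given baseline, which is not the same as equal raw improvement. When ρ is below 1 and SDs are equal, people with a high baseline show larger raw improvement under this null. The distinction is correct. Conditioning on baseline is nevertheless what the parent models do, so it is the consistent choice, provided results are described as baseline-adjusted.

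**Conclusion.** The point holds as an avoidable weakness in an exploratory sub-study. As written, Aim 2 has no baseline term, and its stated purpose goes beyond what a correlation with a follow-up score can show. If the Day 60 score is used as recorded, a code that marks only starting pain is flagged in roughly 11% to 42% of samples of 30 for r 0.3 to 0.5 and ρ 0.5 to 0.7, instead of about 5%. Noisier counts lower these rates (16% to 27% at r = 0.5) and stronger links raise them (about 74% at r = ρ = 0.7). There is no inflation if either link is absent.

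A reader might infer that baseline adjustment would make the result a finding about efficacy. It would not: the intended interviewees all received skills-based VR, and interviews follow the Day 60 survey, so the pain outcome may shape what people say. Nor does the point bear on the trial's primary or secondary results.

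**What to change.** In section 13.2 Aim 2, name the outcome as the PROMIS Pain Interference T-score at Day 60 (parent study) or week 8 (concurrent study). Replace the plain correlation with a partial Spearman correlation between code frequency and that score, given the participant's own baseline PROMIS Pain Interference. Do not substitute an unadjusted change score.

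Confirm that the concurrent study holds a comparable baseline; these documents do not show one. If it does not, run the adjusted analysis on interviewees who have a baseline and report how many that is.

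In the closing paragraph of Aim 2, describe results as association with baseline-adjusted pain interference within the skills-based arm, not as effects on efficacy.

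The cost is about two sentences and one degree of freedom (28 to 27 at n = 30). Parent-study participants need no new data, since the Schedule of Activities already collects the score before randomization.
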